## SCHEDULE OF EVENTS

PROCEDURES	Visit 1 Screening (Days -45 to -14)	Visit 2 Baseline Day 1	Visit 3 Day 7 ± 1	Visit 4 EOS  Day 14 ± 2
Informed Consent/Assent	X	X 		
Demographics	X			
Inclusion/Exclusion Criteria	X	Reconfirm eligibility		
Medical/Dermatological History	X			
Dermatologic Exam	X			
Physical Exam	X			X
Vital Signs, Height, and Weight 	X			X
UPT  (females of childbearing potential)	X	X		X
ECG	X			X
Safety Labs (Hematology, Chemistry and Urinalysis) 	X			X
Urine Drug Screen	X			
Virus Screen (HIV, HCV, HBV)	X			
Investigator's Global Assessment	Confirm eligibility	X		X
Lesion Counts	Confirm eligibility	X		
LSR Assessment		X (pre- & post-application)	X	X
PK Blood Draws 	X	X	X	X
Cosyntropin Stimulation Test (CST) 	X	Confirm eligibility		X
Study Medication Dispensed & Collected 		X	X	X
Study Treatment (q. 12 hours)		X	X 	
Percent BSA to be treated		X		
Weigh Test Article/Verify Compliance		X	X	X
AEs Evaluation	X	X	X	X
Review of Concomitant Medications & Procedures	X	X	X	X

 Subjects who terminate early shall complete all final visit activities designated at Day 14 with the exception of the PK blood draws.

 Subjects who were consented for longer than 45 days prior to the Baseline Visit will be re-consented prior to enrolling into the treatment phase of the trial.

 Height and weight at Visit 1 only.

 Testing will be conducted on all females of childbearing potential. UPT minimal sensitivity is 25 mIU/mL.

 Laboratory test results will indicate if the subject was fasting. Screening laboratory tests will be conducted with the subject fasting and EOS laboratory tests are preferred to be in a fasting state.

 PK blood draws at Visit 3 and Visit 4 will occur 12 hours (± 30 minutes) after the evening application on the prior day.

 CST will be performed at Visits 1 and 4 as indicated. If results at the Day 14 visit show an abnormal CST response, testing will be performed at 4-week intervals until CST response has been documented to return to normal.

 Instruct subject on test article application and provide instruction sheet.

 Withhold morning application until after trough PK blood draw.

## ABBREVIATIONS

AE	Adverse Event
ALT	Alanine Aminotransferase
AST	Aspartate Aminotransferase
β-HCG	Beta-Human Chorionic Gonadotropin
b.i.d.	Twice a day
BMI	Body Mass Index
BSA	Body Surface Area
BUN	Blood Urea Nitrogen
CLIA	Clinical Laboratory Improvement Amendments
CFR	Code of Federal Regulations
CK	Creatine Kinase
CO 2	Bicarbonate
CRF	Case Report Form
CRO	Contract Research Organization
CST	Cosyntropin Stimulation Test
CTCAE	Common Terminology Criteria for Adverse Events
DCF	Data Clarification Form
DLT	Dose Limiting Toxicity
ECG	Electrocardiogram
eCRF	Electronic Case Report Form
EDC	Electronic Data Capture
EOS	End of Study
EU	European Union
FDA	Food and Drug Administration
GGT	Gamma-Glutamyl Transferase
HBV	Hepatitis B Virus
HCV	Hepatitis C Virus
HIV	Human Immunodeficiency Virus
HPA	Hypothalamic-Pituitary-Adrenal
I/E	Inclusion/Exclusion
IEC	Institutional Ethics Committee
IGA	Investigator's Global Assessment
IND	Investigational New Drug
IRB	Institutional Review Board
IUD	Intrauterine Device
LDH	Lactate Dehydrogenase
LSR	Local Skin Reaction
MCH	Mean Corpuscular Hemoglobin
MCHC	Mean Corpuscular Hemoglobin Concentration
MCV	Mean Corpuscular Volume
MedDRA	Medical Dictionary for Regulatory Activities
mL	Milliliter

mIU	Milli International Units
µg/dL	Micrograms/deciliter
NCI	National Cancer Institute
OTC	Over-the-Counter
PK	Pharmacokinetics
PT	Preferred Term
QA	Quality Assurance
RBC	Red Blood Cells
RDW	Red Blood Cell Distribution Width
SAE	Serious Adverse Event
SGOT	Serum Glutamic Oxaloacetic Transaminase
SGPT	Serum Glutamic Pyruvic Transaminase
SOC	System Organ Class
●	●
UPT	Urine Pregnancy Test
US	United States
USP	United States Pharmacopeia
WBC	White Blood Cells

## 1. BACKGROUND

CB-03-01 (cortexolone 17 $\alpha$ -propionate) is a steroidal antiandrogen that is being developed as a cream for the topical treatment of acne vulgaris, an androgen-dependent skin disorder. CB-03-01 binds to the human androgen receptor displacing the androgenic hormones and acts as an androgen antagonist. In human plasma, CB-03-01 is rapidly metabolized to parent cortexolone so that its systemic bioavailability after topical application is anticipated to be low. Cortexolone, the main by-product, is a physiological component of the pool of endogenous corticosteroids, and is an intermediate in the synthesis of glucocorticoids, but it only exhibits weak glucocorticoid properties [[2\\_References](#)].

To date, four Phase 1 and three Phase 2 clinical studies have been completed with CB-03-01 cream in Europe and the United States, with over 500 subjects exposed to CB-03-01 creams. All studies were conducted using CB-03-01 cream, 1%; additional concentrations of CB-03-01 cream (0.1% and 0.5%) were also used in the most-recent Phase 2 Dose-Escalating study. The studies included:

1. A Phase 1 Single Dose Pharmacokinetics (PK) Study in 24 healthy volunteers [randomized, double-blind, vehicle-controlled, single-ascending dose],
2. A Phase 1 Repeat Dose PK Study in 24 healthy volunteers [randomized, vehicle-controlled, 14-day repeat-dose],
3. A Phase 1 Steady State PK Study in 8 subjects with acne vulgaris [single center, open-label, pilot, 6-week repeat-dose]
4. A Phase 1 Three-week Cumulative Skin Irritation Study in 36 healthy volunteers,
5. A Phase 2 HPA/PK study in 42 subjects with acne vulgaris [open-label, 14-day repeat-dose]
6. A Phase 2 Comparator Proof of Concept Study in 72 adult subjects with facial acne vulgaris [randomized, double-blind, vehicle-controlled, active-comparator (Retin-A® [tretinoin] 0.05% cream), 8-week repeat-dose], and
7. A Phase 2 Dose-Escalating Study in 363 subjects with facial acne vulgaris [multi-center, randomized, double-blind, vehicle controlled, 12-week repeat-dose]

Overall, the data that resulted from the completion of the aforementioned studies has demonstrated that CB-03-01 creams selected for clinical development (a) are well tolerated locally, (b) result in minimal systemic exposure when applied topically, (c) have a clinical safety profile without any concern and similar to the vehicle, and (d) at 1% concentration applied b.i.d. are significantly more effective than its vehicle at reducing inflammatory and non-inflammatory lesions counts in adolescent and adult subjects.

Two Phase 3, randomized (1:1), double-blind, vehicle-controlled studies have been initiated in subjects 9 years of age and older with moderate to severe acne vulgaris. In each study, approximately seven hundreds subjects will be treated twice daily for 12 weeks with either CB-03-01 cream, 1% or vehicle cream.

CB-03-01 could offer advantages over existing products for acne vulgaris due to its potential efficacy and lack of systemic antiandrogen activity. Because its pharmacological action appears to be limited to the local site of application, use of CB-03-01 may be able to mitigate the side effects related to systemic exposure to hormonal agents currently used in the treatment of acne.

## 2. RATIONALE

This study was designed to investigate the safety (adrenal suppression effects and systemic concentrations of the drug product) of CB-03-01 cream, 1% in subjects 9 to <12 years of age with facial acne vulgaris. Adrenal suppression effects and systemic safety are an important safety concern. The current study was designed to investigate these concerns. Based on the results of Study 171-7151-202, a Phase 2, open label, maximal use HPA/PK study that was conducted in 42 subjects [twenty-two (22) adolescents (12 to <18 years of age) and twenty (20) adults ( $\geq 18$  years of age)] with moderate to severe acne vulgaris of the face and chest/back (the “Treatment Area”), few subjects (1/20 adults [5.0%] and 2/22 [9.1%] adolescents) demonstrated laboratory evidence of adrenal suppression and no subjects demonstrated any clinical evidence of adrenal suppression [[3\\_References](#)]. Additionally, systemic exposure to CB-03-01 was low per the PK evaluation.

## 3. OBJECTIVE

The primary objectives of this study are to determine a) the adrenal suppression potential and b) the trough plasma concentrations associated with topical application of CB-03-01 cream, 1% in subjects with acne vulgaris.

## 4. STUDY DESIGN

This is an open-label, multicenter study in approximately 20 subjects 9 to <12 years of age with moderate to severe facial acne vulgaris (IGA score of 3 or 4) and obvious acne on the trunk (i.e., shoulders, upper chest, and/or back). The study will include a Screening Visit, a Baseline Visit, and two (2) scheduled follow-up visits. Eligible subjects will be dispensed CB-03-01 cream, 1% and will be instructed how and where to apply the test article to the face and trunk (see [Section 6.2](#) for definition of the “Treatment Area”) every 12 hours for two (2) weeks. Subjects will apply 2 grams of the test article per application. The test article will be applied by the subject or subject’s parent/guardian in the clinic under supervision on Day 1 and Day 7 and at home for all other applications. The Medical Monitor will consider Dose Limiting Toxicity (DLT) when reviewing the safety data (see [Section 8](#)).

## 5. STUDY POPULATION

Male and female subjects 9 to <12 years of age with moderate to severe facial acne vulgaris (IGA of Grade 3 or 4) and obvious acne on the trunk (i.e., shoulder, upper chest, and/or back) will be enrolled into the study. Subjects will be enrolled at approximately six sites in the United States and Poland.

## 5.1 Subject Eligibility

To be included in the study, subjects must meet the following inclusion and none of the exclusion criteria.

### 5.1.1 Inclusion Criteria

1. Subject is male or female 9 to <12 years of age at the time of consent/assent.
2. Subject must provide written informed assent and be accompanied by the parent or legal guardian at the time of assent/consent signing. The parent or legal guardian must provide written informed consent for the subject.
3. Females of childbearing potential must be using highly effective birth control methods with a negative urine pregnancy test (UPT) at the Screening and Baseline Visits.
4. Subject has moderate to severe facial acne vulgaris (Grade 3 or 4) as determined by the Investigator's Global Assessment (IGA) [0 (clear) to 4 (severe) scale] and obvious acne on the trunk (i.e., shoulders, upper chest, and/or back) at the Screening Visit.
5. Subject has facial acne vulgaris with a minimum of 15 inflammatory lesions (papules, pustules, and nodules/cysts) and a minimum of 15 non-inflammatory lesions (open and closed comedones) at the Screening Visit.
6. Subject must be in general good health in the opinion of the investigator, with normal renal function as defined per protocol and no clinically relevant abnormalities present at the screening physical examination, in the subject's medical history, or from safety laboratory tests (hematology, serum chemistry, and urinalysis).
7. Subject has normal adrenal function with a Cosyntropin Stimulation Test (CST) at Screening, defined as a normal pre-stimulation cortisol level and a 30-minute post-stimulation cortisol level of >18 µg/dL.
8. Subject and parent/guardian are able to communicate with the staff and are willing to comply with study instructions, reside at and/or return to the clinic for required visits.

---

 Females of childbearing potential are defined as subjects who have experienced menarche or are 10 years of age or older. Note: If a female becomes 10 years of age during the study, she must have a negative UPT at that time to continue study participation.

 Highly effective contraception includes: a) intrauterine device (IUD) for at least one week prior to Visit 2 (Baseline); b) hormonal contraceptives (injections, implants, transdermal patch, vaginal ring); c) partner vasectomy (performed at least six months prior to Visit 2 [Baseline]); d) oral contraceptives WITH a barrier method: i) Male or female condom; diaphragm with spermicides; cervical cap with spermicides; contraceptive sponge e) two barrier forms of contraception: i) male or female condom; ii) diaphragm with spermicides; iii) cervical cap with spermicides; iv) contraceptive sponge; OR f) total abstinence.

 Females taking hormonal therapy for any reason exclusive for the treatment of acne (e.g., as contraception, etc.) must be on treatment for at least 12 weeks prior to study entry and must not change their dosing regimen during the study. Those who have used hormonal therapy prior to study entry must have discontinued use at least eight weeks prior to the start of the study.

 Normal renal function (per the requirement of inclusion criterion #6) is defined as a creatinine clearance of 80 mL/min or greater based on serum creatinine and the Cockcroft and Gault equation [1].

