## PROTOCOL SYNOPSIS

Title	An Open Label Evaluation of the Adrenal Suppression Potential and Trough Plasma Concentrations of Cortisolone 17 $\alpha$ -Propionate (CB-03-01) Cream Applied Every 12 Hours for Two Weeks in Subjects 9 to <12 Years of Age with Acne Vulgaris
Protocol Number	CB-03-01/28
Study Type	Phase 2
Test Article(s)	CB-03-01 cream containing 1% cortisolone 17 $\alpha$ -propionate
Study Objective	The primary objectives of this study are to determine: a) the adrenal suppression potential and b) the trough plasma concentrations associated with topical application of CB-03-01 cream, 1% in subjects with acne vulgaris.
Study Design	An open label, multicenter study in children 9 to <12 years of age.
Treatment Groups	Eligible subjects will be dispensed CB-03-01 cream, 1% and will be instructed how and where to apply the test article to the face and trunk (see Section 6.2 for definition of the "Treatment Area") every 12 hours for two (2) weeks. Subjects will apply 2 grams of the test article. The test article will be applied by the subject or subject's parent/guardian in the clinic under supervision on Day 1 and Day 7 and at home for all other applications.
Duration of Treatment	Approximately 2 weeks
Duration of Study	Approximately 4-6 weeks
Study Population	Male and female subjects 9 to <12 years of age with moderate to severe facial acne vulgaris (Grade 3 or 4 on the Investigator's Global Assessment [IGA]) and obvious acne on the trunk (i.e., shoulder, upper chest, and/or back).
Total Number of Subjects	At least twenty (20) evaluable subjects. This may require the enrollment of approximately 24 subjects.
Number of Sites	Approximately six sites in the United States and Poland.
Inclusion Criteria	To enter the study, a subject must meet the following criteria: 

1. Subject is male or female, 9 to <12 years of age at the time of consent/assent.

2. Subject must provide written informed assent and be accompanied by the parent or legal guardian at the time of assent/consent signing. The parent or legal guardian must provide written informed consent for the subject.

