### **5.1.2 Exclusion Criteria**

1. Subject is pregnant, lactating, or is planning to become pregnant during the study.
2. Subject has a Body Mass Index (BMI) for age percentile >95% (see [Appendix 5](#)).
3. Except for the use of contraceptives, subject reported use of any prescription drug or herbal product within two (2) weeks of Visit 2 (Baseline), any non-prescription drug or vitamin or mineral supplements within one (1) week of Visit 2 (Baseline); any known enzyme-inducer, enzyme-inhibitor, or reported chronic exposure to enzyme-inducers such as paint solvents or pesticides within 30 days of Visit 2 (Baseline).
4. Subject has used topical anti-acne medications containing retinoids such as tazarotene, adapalene, or tretinoin within four (4) weeks of Visit 2 (Baseline).
5. Subject has used the following systemic anti-acne medications: antibiotics within two (2) weeks of Visit 2 (Baseline), spironolactone within four (4) weeks of Visit 2 (Baseline), or retinoid therapy within three (3) months of Visit 2 (Baseline).
6. Subject has used topical corticosteroids (including inhaled and intranasal corticosteroids) within two (2) weeks of the CST at Visit 1 (Screening) and/or between Visit 1 (Screening) CST and Visit 2 (Baseline).
7. Subject has used systemic corticosteroids (including intramuscular and intralesional injections) within four (4) weeks of the CST at Visit 1 (Screening) and/or between the Visit 1 (Screening) CST and Visit 2 (Baseline).
8. Subject has used light treatments, microdermabrasion or chemical peels to the face, chest, and/or back within eight (8) weeks of Visit 2 (Baseline).
9. Subject has any skin or medical condition, including facial hair that could interfere with the evaluation of the test article or requires the use of interfering topical or systemic therapy.
10. Subject has any condition which, in the investigator's opinion, would make it unsafe for the subject to participate in this research study.
11. Subject has the need or plans to be exposed to artificial tanning devices or excessive sunlight during the study.
12. Subject cannot avoid any type of strenuous exercise (swimming, running, team sports, etc.) or the use of hot tubs/saunas from Visit 2 (Baseline) to the end of the study (Visit 4).

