### **6.2 Instructions for Use and Application**

Mild soap will be dispensed to the subject at Visit 1/Screening, which must be used for washing the Treatment Area and other areas of the body throughout the study; the subject must, at a minimum, begin using the provided mild soap in the morning prior to the clinic visit on Day 1 (i.e., Visit 2).

The subject and parent/guardian will be instructed to wash the area(s) to be treated (i.e., face and trunk) in the morning prior to clinic visits with the mild soap and water and then dry the area gently. At the clinic, the study staff will then instruct the subject and parent/guardian on how to dispense the test article and where to apply the test article. The

“Treatment Area” will be defined at Visit 2/Baseline by the investigator as the area to which the test article is applied and will include the face and trunk. The test article will be applied to the entire face and areas of the trunk (i.e., shoulders, upper chest, and/or upper back) where acne is present. The entire 2 grams of the test article must be applied; thus, if there is still test article remaining after the affected area of the trunk is treated, the test article will be applied to the adjacent skin. The subject will be instructed to apply the test article to this same Treatment Area with each application, regardless of whether acne is still present. The percent BSA of the Treatment Area will be recorded at Baseline.

The first application of test article will be applied in the clinic under supervision of the study staff. The staff will dispense 2 grams of the test article; the subject will then be instructed (with assistance from parent/guardian, if necessary) to apply the test article to the defined Treatment Area using the “Dab, Spread, Pat” method of application. Subjects will be instructed to dab small amounts of the test article using a fingertip gently on the areas to be treated, then spread the test article to provide a thin, uniform layer over the entire Treatment Area, and finally to gently pat the skin until the test article has been absorbed into the skin. The study staff must assure that the subject (or with assistance from parent/guardian) is able to apply the test article to the entire Treatment Area (including the back).

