7.2.2 Evaluable Population

The evaluable population will include those subjects in the safety population who have both Screening and Day 14 serum cortisol data (pre- and post-cosyntropin stimulation) and meet the following criteria:-

- Meets all inclusion/exclusion criteria, including normal response to cosyntropin stimulation defined as a Screening CST with a 30-minute post-stimulation cortisol level of > 18 µg/dL.
- Screening and Day 14 CST were conducted between 7-9 AM.
- Day 14 CST was conducted within ±1 hour of the Screening CST.
- Applied at least 80% of expected applications and applied the final dose no more than 14 hours prior to the start of the CST test.
- Has not taken or applied any medications that may interfere with HPA axis function.
- Do not have any other significant protocol deviations.

HPA axis suppression analysis will be conducted on the Evaluable population.

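### The renal entry rule is not indexed to body size, so at a given creatinine it acts as a minimum weight and may exclude some light healthy children, mainly girls

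*Protocol*

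**What the plan says.** Protocol Section 5.1.1 sets the age range ("Subject is male or female 9 to <12 years of age at the time of consent/assent") and, in inclusion criterion 6, requires good general health "with normal renal function as defined per protocol". Footnote 19, and footnote 4 in the Synopsis, give that definition: a "creatinine clearance of 80 mL/min or greater based on serum creatinine and the Cockcroft and Gault equation". The equation is cited but not written out. No reason is given for the equation, the cut-off or the lack of body-size indexing.

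The dose does not depend on body size. Section 4 states: "Subjects will apply 2 grams of the test article per application". Section 6.2 adds: "The entire 2 grams of the test article must be applied", with any excess going on adjacent skin. The only explicit body-size limit is an upper one in Section 5.1.2: "Subject has a Body Mass Index (BMI) for age percentile >95" (percent).

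SAP Section 7.2.2 carries the entry rules into the adrenal analysis, because the Evaluable population requires: "Meets all inclusion/exclusion criteria, including normal response to cosyntropin stimulation". SAP Section 7.7.3 summarises weight for the Safety population only. For screen failures, SAP Section 7.7.1 plans a listing of demographic data, and Protocol Section 18.3 plans a summary of the primary reason for failure. Neither document plans a subgroup analysis or any summary per kilogram.

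**The concern.** An absolute clearance that rises in proportion to weight measures body size as well as kidney function. Age hardly varies in this study, so a child's result is driven by weight divided by creatinine. A small child with unremarkable creatinine can fall below 80 mL/min because she is small.

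This touches the study's purpose. The objectives in Protocol Section 3 are adrenal suppression potential and trough plasma concentrations. With a fixed amount of cream, the lightest children receive the most drug per kilogram applied, and they are the ones this rule can remove. A study of suppression potential has reason to want them represented. The protocol sets no deliberate lower weight limit, so this one appears unintended. The planned outputs would not show it: a reader of the report would see that a child failed criterion 6, but not her weight or computed clearance.

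**Working it through.** The documents derive no figure from the 80 mL/min cut-off, so there is nothing to reproduce. The check asks what the rule implies.

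**Inputs from the documents.** Cut-off 80 mL/min (footnotes 4 and 19); age 9 to under 12 (criterion 1); 2 g every 12 hours (Section 4); 1% strength (Synopsis).

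**Assumptions.** The equation is taken as clearance = (140 − age) × weight / (72 × creatinine), multiplied by 0.85 in females, with weight in kg and creatinine in mg/dL. A creatinine range of 0.4 to 0.7 mg/dL is used.

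**Step 1: the role of age.** (140 − age) runs only from 131 at age 9 to just above 128 below age 12, a spread of about 2%.

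**Step 2: minimum weight to pass.** Solving for weight gives 80 × 72 × creatinine / (140 − age), divided by 0.85 for girls. At age 10 this is 5760/130 = 44.3 × creatinine for boys and 44.3/0.85 = 52.1 × creatinine for girls. The floor is about 18% higher for girls (1/0.85 = 1.18).

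**Step 3: applied dose at that floor.** 2 g × 1% × 2 applications = 40 mg/day, divided by weight.

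| Creatinine (mg/dL) | Boys: minimum kg | mg/kg/day there | Girls: minimum kg | mg/kg/day there |
|---|---|---|---|---|
| 0.4 | 17.7 | 2.26 | 20.9 | 1.91 |
| 0.5 | 22.2 | 1.80 | 26.1 | 1.53 |
| 0.6 | 26.6 | 1.50 | 31.3 | 1.28 |
| 0.7 | 31.0 | 1.29 | 36.5 | 1.10 |

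**Step 4: worked cases, age 10.**
- Girl, 25 kg (1.60 mg/kg/day): 130 × 25 × 0.85 / (72 × creatinine) = 96 at 0.4 (passes), 77 at 0.5 and 64 at 0.6 (fails both).
- Boy, 25 kg: 113, 90 and 75 at the same values, so he fails only at 0.6.
- Girls with creatinine 0.6: 28 kg scores 72 and fails; 40 kg scores 102 and passes. Only weight differs.
- Any child of 40 kg (1.00 mg/kg/day) passes throughout 0.4 to 0.7; the lowest score is 88.

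**Step 5: how many children might be affected.** The documents give no weight or creatinine distribution, so a simulation used assumed ones: log-normal weight with median 32, 36 or 40 kg and log-scale SD 0.2; creatinine mean 0.45 to 0.60 with SD 0.08; correlation between them 0 or 0.4; half girls; age uniform over 9 to 12. Across these settings:
- 0.2% to 34% of children are excluded, and always a larger share of girls than boys;
- 1% to 79% of the lightest quarter are excluded;
- mean applied mg/kg/day is 0.1% to 9% lower among those admitted than among all.

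In a middle setting (median 36 kg, mean creatinine 0.50), 2.7% to 6.1% are excluded overall, 10% to 22% of the lightest quarter, and mean applied dose moves from 1.13 to between 1.11 and 1.12 mg/kg/day.

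**The case against.** The strongest reply is that no effect on the results has been shown, and that is correct. A reader might infer that the rule biases the suppression rate and trough levels low. The documents do not support that: they give no screen-failure rate and no relation between applied mg/kg and trough level or cortisol response. This is a topical product spread over an area that varies by child, and Protocol Section 1 expects rapid metabolism and low systemic bioavailability, so applied mg/kg is not absorbed dose. The assumed shift in the mean is also small beside the precision of the study: with 20 evaluable children the exact 95% interval is 0 to 16.8% for 0/20 and 0.1% to 24.9% for 1/20.

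A reader might also infer that small children are excluded as a class, or that the top of the mg/kg range is cut off. The table says otherwise. At creatinine 0.4 a girl of about 21 kg passes, at 1.91 mg/kg/day. The rule thins out light children with higher creatinine; it does not remove all light children.

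A third tempting reading is that a heavy child with impaired kidneys could slip through. Other rules largely cover this: criterion 6 also requires no clinically relevant laboratory abnormality, creatinine and BUN are on the panel (Section 13.1), exclusion 13 bars clinically significant renal disease, and Section 14.4 screen-fails clinically significant out-of-range results.

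What remains is the definition itself. A small change in the mean does not answer the concern about the lightest children, and nothing in either document justifies a size-dependent renal rule at this age.

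**Conclusion.** The point holds as a design weakness of uncertain size. Both footnotes make an unindexed clearance a binding entry rule. Given the assumed form of the equation, it acts at any fixed creatinine as an undeclared minimum weight that is higher for girls, and it may exclude some light healthy children, mainly girls at about 0.5 mg/dL or more. Because the dose is fixed, the study could under-represent the top of the applied-dose range, and SAP Section 7.2.2 means that enrolling such a child in breach of the rule would not bring her into the adrenal analysis.

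The weight floors are firm once the equation is accepted. The share excluded rests wholly on assumed weight and creatinine distributions and could be negligible or substantial. No direction or size of error in the suppression proportion or trough concentrations is established.

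**What to change.** In Protocol footnotes 4 and 19, replace the definition with an age-appropriate renal estimate indexed to body size. Height (Section 10.1) and serum creatinine (Section 13.1) are already collected at Screening. The sponsor should choose and justify both the equation and the cut-off.

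In the SAP, list weight, creatinine and computed clearance for every child screen-failed on criterion 6, and summarise weight and applied mg/kg/day for the Evaluable and PK populations. This reporting is worth adding even if the footnotes stay as they are.

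Apply the new definition prospectively. Reconsider earlier renal screen failures only if Baseline can still fall within the 14 to 45 days after the Screening CST that Section 10.2 requires. Beyond that, a child would need a repeat cosyntropin test, which this point does not justify.

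The cost is a protocol amendment to one definition in two places, a matching change to any eligibility calculation in the eCRF, and a few extra outputs. No new procedure is needed for children screened from then on. The drawback is that children screened before and after the amendment are judged by different formulas; the listing should show which one applied.
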